6.2. Summary of Deaths and Other Serious Adverse Events

Table 14.3.2.1.1
Serious Adverse Events by System Organ Class and Preferred Term
Safety Population

Programming Notes:

- Same shell as Table 14.3.1.2. Change first row to be "Number of Subjects with at Least One SAE", add "SAE = Serious Adverse Event" to abbreviations, and remove references to TEAEs.
- Change footnote for "Reference Table 14.3.3.1".
- A column for column

Table 14.3.2.1.2
Life-Threatening Serious Adverse Events by System Organ Class and Preferred Term Safety Population

Programming Notes:

- Same shell as Table 14.3.1.2. Change first row to be "Number of Subjects with at Least One Life-Threatening SAE", add "SAE = Serious Adverse Event" to abbreviations, and remove references to TEAEs.
- Add "Note: Life-threatening SAEs as judged by the investigator".
- Change footnote for "Reference Table 14.3.3.1".
- A column for column dosing (column for column for col

Final 1.0 | 12-Jul-2023 | Page 68 of 205

[figure not shown]

Table 14.3.2.1.3 Serious Adverse Events with Outcome Death by System Organ Class and Preferred Term Safety Population

Programming Notes:

- Same shell as Table 14.3.1.2. Change first row to be "Number of Subjects with at Least One SAE with Outcome Death", add "SAE = Serious Adverse Event" to abbreviations, and remove references to TEAEs.
- Change footnote for "Reference Table 14.3.3.2".
- A column for column dosing (CC) will only be added if Stage 4 is initiated.

Table 14.3.2.1.4
Serious Adverse Events by Relationship to Study Medication, System Organ Class and Preferred Term Safety Population

Programming Notes:

- Same shell as Table 14.3.1.4. Change first row to be "Number of subjects with at Least One SAE", add "SAE = Serious Adverse Event" to abbreviations, and remove references to TEAEs.
- Change footnote for "Reference Table 14.3.3.1".
- A column for column dosing (column dosing (column dosing (column dosing (column dosing dosing dosing (column dosing dos

Final 1.0 | 12-Jul-2023 | Page 69 of 205

[figure not shown]

Table 14.3.3.1 Listing of Serious Adverse Events Safety Population

[figure not shown]
Subject ID/ Treatment Arm	AE ID Number	System Organ Class/ Preferred Term/ Verbatim Term	Start Date/Time (Study Day)/ End Date/Time (Study Day)	Severity/ Relationship	Outcome/ Action Taken/ Therapy?	SAE Leading to Study DC?		Serious Criteria
XXXXX/ XXXX	X	XXXXXXXXXX/ XXXXXXXXXXXXX XXXXXXXXXXX	DDMMMYYYY/ HH:MM (X)/ DDMMMYYYY/ HH:MM (X)	XXXXXXXX/ XXXXXXXX	XXXXXXXXXX/ XXXXXXXXXX/ Yes	No	No	XX
XXXXX/ XXXX	X	XXXXXXXXXXXXXXXXXXXXXXXXXXXXXXXXXXXXXX	DDMMMYYYY/ HH:MM (X)/ DDMONYYYY /HH:MM (X)	XXXXXXXXX/ XXXXXXXX	XXXXXXXXXX/ XXXXXXXXXX/ No	Yes	XX	XX / XXX
XXXXX/ XXXX	X	XXXXXXXXXXXXX/ XXXXXXXXXXXXX XXXXXXXXXX	DDMONYYYY/ HH:MM (X)/ Ongoing	XXXXXXXXX/ XXXXXXXX	XXXXXXXXXX/ XXXXXXXXXX/N o	No	XX	XX / XXX

DC = discontinuation; ID = identification; IP = investigational product; MedDRA = Medical Dictionary for Regulatory Activities; SAE = serious adverse event; TEAE = treatment emergent adverse event.

Note: Study Day = date of interest – date of first infusion. A TEAE is defined as an adverse event with an onset at the time of or following the start of treatment with IP.

SAEs were coded using MedDRA version 26.0

Final 1.0 | 12-Jul-2023 | Page 70 of 205

- If time missing, display "- -:- -".
- AE ID number represents Record position within Subject.
- If no events meet the criteria for display (i.e., no AEs occur in the study), present "No events are reported.".
- SOC & PT text should be in proper case in table.
- Sort by Treatment ID/ Subject ID / Start Date / End Date (alphabetically for SOC if same date for two events).
- In case a term is not coded (e.g., in a dry run) it will be labelled as "Not Coded [SOC]" and "Not Coded [PT]". SOC and PT abbreviations should be added in this case in footnote.

Final 1.0 | 12-Jul-2023 | Page 71 of 205

[figure not shown]

Table 14.3.3.2 Listing of Deaths Safety Population

[figure not shown]
Subject ID/ Treatment Arm	AE ID Number	System Organ Class/ Preferred Term/ Verbatim Term	Start Date/Time (Study Day)/ End Date/Time (Study Day)	Severity/ Relationship	Outcome/ Action Taken/ Therapy?	AE Leading to IP DC?	TEAE?	Serious Criteria
XXXXX/ XXXX	X	XXXXXXXXXXXXXXXXXXXXXXXXXXXXXXXXXXXXXX	DDMMMYYYY/H H:MM (X)/ DDMMMYYYY/H H:MM (X)	XXXXXXXX/ XXXXXXXX	XXXXXXXXXX/ XXXXXXXXXX/ Yes	No	No	XX
XXXXX/ XXXX	X	XXXXXXXXXXXXXX/ XXXXXXXXXXXXXXXXXXXXXX	DDMMMYYYY/H H:MM (X)/ DDMMMYYYY/H H:MM (X)	XXXXXXXX/ XXXXXXXXX	XXXXXXXXX/ XXXXXXXXX/No	Yes	XX	XX / XXX
XXXXX/ XXXX	X	XXXXXXXXXXXXXXXXXXXXXXXXXXXXXXXXXXXXXX	DDMMMYYYY/H H:MM (X)/ Ongoing	XXXXXXXX/ XXXXXXXX	XXXXXXXXX/ XXXXXXXX/ No	No	XX	XX / XXX

DC = discontinuation; ID = identification; IP = investigational product; MedDRA = Medical Dictionary for Regulatory Activities; TEAE = treatment emergent adverse event.

Note: Study Day = date of interest – date of first infusion. A TEAE is defined as an adverse event with an onset at the time of or following the start of treatment with IP.

AEs were coded using MedDRA version 26.0

[figure not shown]
Final 1.0 | 12-Jul-2023 | Page 72 of 205

- If time missing, display "- -:- -".
- AE ID number represents Record position within Subject.
- If no events meet the criteria for display (i.e., no AEs occur in the study), present "No events are reported.".
- SOC & PT text should be in proper case in table.
- Sort by Treatment Arm/ Subject ID / Start Date / End Date (alphabetically for SOC if same date for two events).
- In case a term is not coded (e.g., in a dry run) it will be labelled as "Not Coded [SOC]" and "Not Coded [PT]". SOC and PT abbreviations should be added in this case in footnote.

Final 1.0 | 12-Jul-2023 | Page 73 of 205

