2.2.4. Other Endpoints

The following endpoints will be assessed:

- Change in the weekly average of the average daily pain scores from the baseline week to Week 12, as measured on an 11-point (0-10) NRS, versus dose.
- Immunogenicity (ADA) assessments.

3. Overall Study Design and Plan

This is a randomised, double-blind, placebo-controlled study of MEDI7352 in subjects with moderate to severe chronic PDN persistent for 6 months or longer, not adequately controlled by standard of care treatments, caused by type 1 or type 2 diabetes mellitus. The study incorporates a screening period of up to 45 days and a 12-week double-blind treatment period during which MEDI7352 or placebo will be administered intravenously (IV) on 6 occasions, with each dose separated by 14 days. There will be a 6-week follow-up period.

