6.1.8. Derived Variables

- Change from baseline = value at current time point value at baseline.
- Reference End Date = Date of completion/discontinuation.
- Study duration = Reference end date date of first dose of treatment + 1
- Duration of exposure (days) = min(date of last dose of treatment + 14 days or date of death) date of first dose of treatment + 1.
- Treatment-emergent AEs (TEAEs) are defined as:
 - o AEs with onset at the time of or following the start of treatment with IP, or
 - AEs starting prior to the start of treatment but increasing in severity or relationship at the time of, or following, the start of treatment with IP.
- Average Baseline Pain NRS = the arithmetic average of the 'non-missing' daily pain scores within the baseline period defined in Section 6.1.1. For example, if a subject has 5 days of non-missing pain scores their average will be calculated over 5 days, not the full 7-day baseline period.
- Average Week X Pain NRS = the arithmetic average of the 'non-missing' daily pain scores within each subject's specific week X period defined in Section 6.1.5.
- Average Week 12 Pain NRS (LOCF) = the arithmetic average of the 'non-missing' daily pain scores within each subject's specific week 12 period or according to the imputed LOCF/BOCF approach defined in Section 6.1.4.
- Change from Baseline to Week X Pain NRS = for each subject 'Average Week X Pain NRS' minus 'Average Baseline Pain NRS'.
- Change from Baseline to Week 12 Pain NRS (LOCF/BOCF) = for each subject 'Average Week 12 Pain NRS (LOCF)' minus 'Average Baseline Pain NRS'.
- Galer NPS Total Score (ranges from 0 to 100): sum of Pain Intensity, Pain Unpleasantness, Pain Sharpness, Pain Hotness, Pain Dullness, Pain Coldness, Pain Sensitivity, Pain Itching, Deep Pain Intensity, and Surface Pain Intensity (All in an 11-point NRS).
- Change from Baseline to Week X Galer NPS Total Score = for each subject 'Galer NPS Total Score' minus 'Baseline Galer NPS Total Score'.
- Total number of days rescue medication was used = End Date of Medication Start Date

of medication + 1. Each day on which rescue medication was used at least once is counted.

- Cumulative consumption (mg) of paracetamol rescue medication use = Total dose of rescue medication (mg) consumed during the days in which paracetamol was used.

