- Update Reference Listing to 16.2.7.2.
- A column for column dosing (Column dosing will only be added if Stage 4 is initiated.

Table 14.3.1.7

Non-Serious Adverse Events Occurring in More than 5% of Subjects by System Organ Class and Preferred Term Safety Population

Programming Notes:

- Same shell as Table 14.3.1.2. Change first row to be "Subjects with at Least One Non-Serious AE" and remove references to TEAEs.
- Update Reference Listing to 16.2.7.1.
- A column for column for dosing (column for dosing

Final 1.0 | 12-Jul-2023 | Page 65 of 205

[figure not shown]

Table 14.3.1.8

Treatment Emergent Adverse Events Occurring in More than 5% of Subjects by Preferred Term Safety Population

			Safety I opulation	I .			
	Placebo	Placebo MEDI7352					
Preferred Term	(N=xx)	(N=xx)	(N=xx)	(N=xx)	All MEDI7352 (N=xx)	(N=xx)	
Subjects with at Least One TEAE	xx (xx.x%) xx	xx (xx.x%) xx	xx (xx.x%) xx	xx (xx.x%) xx	xx (xx.x%) xx	xx (xx.x%) xx	
Preferred Term 1	xx (xx.x%) xx	xx (xx.x%) xx	xx (xx.x%) xx	xx (xx.x%) xx	xx (xx.x%) xx	xx (xx.x%) xx	
Preferred Term 2	xx (xx.x%) xx	xx (xx.x%) xx	xx (xx.x%) xx	xx (xx.x%) xx	xx (xx.x%) xx	xx (xx.x%) xx	
Preferred Term 3	xx (xx.x%) xx	xx (xx.x%) xx	xx (xx.x%) xx	xx (xx.x%) xx	xx (xx.x%) xx	xx (xx.x%) xx	
•••							

 $AE = adverse \ event; IP = investigational \ product; MedDRA = Medical \ Dictionary \ for \ Regulatory \ Activities; n = number \ of \ subjects \ within \ each \ PT \ category;$

N = number of subjects per treatment group; PT = Preferred Term; TEAE = treatment-emergent adverse event.

Note: Results are n (n/Number of subjects in the Safety population within each PT*100) then the total number of events.

A TEAE is defined as AE with an onset at the time of or following the start of treatment with IP.

Aes were coded using MedDRA version 26.0. Subjects are counted once for each PT.

Aes are displayed by descending frequency of PT based on 'All MEDI7352' column, and alphabetically for PT of same frequency. Reference Listing: 16.2.7.1

Programming Notes:

- PT texts should be in proper case in table.
- In case a term is not coded (e.g., in a dry run) it will be labelled as Not Coded [PT]", and sorted at the end of the table.
- A column for column dosing (column for column for col

[figure not shown]

[figure not shown]

Table 14.3.1.9 Treatment Emergent Adverse Events by Preferred Term Safety Population

Programming Notes:

- Same shell as Table 14.3.1.8.
- Display all TEAEs, not only the most common.

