6.3. Displays of Significant Adverse Events and Adverse Events of Special Interest

Table 14.3.2.2.1
Treatment Emergent Adverse Events Associated with Abnormal Liver by System Organ Class and Preferred Term Safety Population

Programming Notes:

- Same shell as Table 14.3.1.2. Change first row to be "Subjects with at least One TEAE Associated with Abnormal Liver". Remove references to TEAEs in footnote.
- Update Reference Listing to 16.2.7.3.
- A column for dosing (CC) will only be added if Stage 4 is initiated.

Table 14.3.2.2.2

Potential joint Related Adverse Events of Special Interest by System Organ Class and Preferred Term Safety Population

Programming Notes:

- Same shell as Table 14.3.1.2. Change first row to be "Subjects with at least One Potential Joint Related AESI"
- Add abbreviation for AESI = Adverse Event of Special Interest. Remove references to TEAEs in footnote.
- Update Reference Listing to 16.2.7.4
- A column for column dosing (CC) will only be added if Stage 4 is initiated.

Final 1.0 | 12-Jul-2023 | Page 74 of 205

[figure not shown]

Table 14.3.2.2.3 Serious and/or severe Infections by System Organ Class and Preferred Term Safety Population

Programming Notes:

- Same shell as Table 14.3.1.2. Change first row to be "Subjects with at Least One SAE or Severe AE Related to Infection". Add "SAE = Serious Adverse Event" to abbreviations. Remove references to TEAEs in footnote.
- Update Reference Listing to 16.2.7.5.
- A column for doing (CC) will only be added if Stage 4 is initiated.

[figure not shown]
Table 14.3.2.2.4

Anaphylactic Reactions, Hypersensitivity or Infusion-Related Reactions Leading to Discontinuation of IP by System Organ Class and Preferred Term Safety Population

Programming Notes:

- Same shell as Table 14.3.1.2. Change first row to be "Subjects with at Least One Anaphylactic Reaction, Hypersensitivity or Infusion-Related Reactions Leading to Discontinuation of IP". Remove references to TEAEs in footnote.
- Update Reference Listing to 16.2.7.6.
- A column for column dosing (cc) will only be added if Stage 4 is initiated.

Final 1.0 | 12-Jul-2023 | Page 75 of 205

[figure not shown]

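### The SAE, common non-serious AE, joint AESI and serious/severe infection tables carry no treatment-emergent condition, so pre-dose events can count as by-arm incidence and no treatment-emergent SAE count by arm is planned

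*SAP*

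**What the plan says.** **SAP text.** Section 9.1 (Adverse Events) asks for the number of subjects with any SAE, and with non-serious AEs above 5%, as lines separate from any TEAE. Section 9.1.2 asks for incidence of SAEs by treatment group, and Section 9.1.4 for incidence of infections meeting SAE or severe criteria. None of these sets an onset window. The scope is the same in SAP v1.0 and v1.1.

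**Shells v1.0.** Tables 14.3.2.1.1 to 14.3.2.1.3 reuse the layout of the general TEAE table, and 14.3.2.1.4 that of the TEAE-by-relationship table. The first row becomes some form of any SAE, and the SAE term is to be added "to abbreviations, and remove references to TEAEs". For Table 14.3.1.7 the first row becomes "Subjects with at Least One Non-Serious AE", followed by "and remove references to TEAEs". For the joint-event table (14.3.2.2.2) the note is "Add abbreviation for AESI = Adverse Event of Special Interest. Remove references to TEAEs in footnote", and the infection table (14.3.2.2.3) has the matching instruction.

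**Definition.** SAP v1.1 Section 6.1.8 counts as treatment-emergent any AE with onset at or after the start of IP, and "AEs starting prior to the start of treatment but increasing in severity or relationship" from that point. Section 10 records that the 30-day upper limit after the last dose was removed.

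**Timeline.** Section 3: "The study incorporates a screening period of up to 45 days", then 12 weeks of treatment and 6 weeks of follow-up.

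**The concern.** These are by-arm incidence tables in the Safety Population, that is, in dosed subjects by actual treatment. Without an onset restriction, an event during screening in a subject who is later dosed appears as incidence in that subject's arm, although neither drug nor placebo can have caused it.

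Three things are at stake:
- Non-causal events in every arm pull between-arm contrasts toward no difference. That matters most for SAEs and for the joint and infection events that the SAP itself names as AESIs.
- Table 14.3.1.7 (all non-serious AEs above 5%) stands next to Table 14.3.1.8 (TEAEs above 5%). A term can pass the cut-off in one and not in the other, with no footnote on onset to explain why.
- No planned table gives treatment-emergent SAEs by arm. The overall AE table (14.3.1.1) has rows for any SAE, related SAEs and SAEs leading to death, but none for treatment-emergent SAEs, and the table lists contain no such table.

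**Working it through.** **Step 1: what the unrestricted tables add.** Under Section 6.1.8 of SAP v1.1 an event is a TEAE if its onset is at or after the first dose (no upper limit), or if it began earlier and then increased in severity or relationship. The complement is therefore an event that began before the first dose and did not increase. For a dosed subject, that is the only kind of event an all-SAE or all-AE table can hold that a TEAE table does not. Under SAP v1.0 the complement also held events starting more than 30 days after the last dose; with the last dose on Day 70, that is after Day 100. Version 1.1 removes that group.

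**Step 2: whether such events are expected.** The second limb of the definition presupposes that AEs starting before treatment are recorded. Listing 16.2.7.1 has a TEAE column, and its sample rows include serious events marked as not treatment-emergent. The deaths listing (Table 14.3.3.2) has a TEAE column too.

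**Step 3: which tables are affected.**
- SAE tables 14.3.2.1.1 to 14.3.2.1.4, Table 14.3.1.7, and Tables 14.3.2.2.2 and 14.3.2.2.3: no onset restriction in title, first row or footnote.
- Table 14.3.2.2.1 ("Treatment Emergent Adverse Events Associated with Abnormal Liver by System Organ Class and Preferred Term Safety Population"): the title and first row keep the restriction; only the defining footnote goes.
- Table 14.3.2.2.4: limited to reactions leading to discontinuation of IP, so post-dose by construction.

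**Step 4: size.** The documents give no count of pre-dose events and do not state when AE recording starts, so what follows is illustration. Assumptions: a constant background rate, full follow-up, and recording from d days before the first dose. Post-dose time is (12 + 6) weeks × 7 = 126 days.

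Pre-dose share of background events = d / (d + 126):
- d = 0: 0%
- d = 7: 7/133 = 5.3%
- d = 14: 14/140 = 10.0%
- d = 45: 45/171 = 26.3%

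Effect on a comparison. Suppose, as an invented example, 4% of placebo and 8% of active subjects have the event after dosing, with 4% per 126 days as the background. The pre-dose risk in either arm is b = 4% × d/126, and the tabulated proportion is 1 − (1 − p)(1 − b).

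| d (days) | b | Placebo | Active | Ratio |
|---|---|---|---|---|
| 0 | 0 | 4.0% | 8.0% | 2.00 |
| 7 | 0.22% | 4.2% | 8.2% | 1.95 |
| 14 | 0.44% | 4.4% | 8.4% | 1.90 |
| 45 | 1.43% | 5.4% | 9.3% | 1.73 |

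Only at the 45-day end does the placebo figure in this example cross 5%. That end is a ceiling, because 45 days is the maximum screening length and a subject with a serious screening event may never be dosed and so never enter the Safety Population.

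**The case against.** The strongest reply is that this is the stated scope and not a slip. Section 9.1 lists any AE, any SAE and non-serious AEs above 5% beside any TEAE, so the authors knew the difference and the shells carry out what the SAP asks. A reader might infer from the notes that the shells dropped a condition imposed by the SAP. The documents do not support that: the SAP never imposed it, so the gap is in the SAP text as much as in the shells.

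Other points on that side:
- **The AESI note edits a footnote.** "Remove references to TEAEs in footnote" is also attached to the liver table, which stays treatment-emergent, so the note alone does not set which events count. That is right. The case for the joint and infection tables rests on their titles, their first rows and the SAP text, none of which restricts onset.
- **The notes are from shells v1.0.** Shells v1.1 exist, but their AE notes are not in the text supplied. This stands as a caveat. The SAP v1.1 body and the v1.1 table titles keep the same scope, so the point does not rest on v1.0 alone.
- **Pre-dose recording is not quantified.** Correct: its start is left to the protocol. Pre-dose onset would also be exceptional for fatal SAEs and for SAEs judged related.
- **TEAE tables exist, and safety is descriptive.** Table 14.3.1.8 gives TEAEs above 5% correctly, and Section 9 plans no safety tests. This limits the harm for common events. It does not supply a treatment-emergent SAE count by arm, which can be recovered only from the flagged listings.

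**Conclusion.** The point holds in a limited form. The SAE tables, the table of non-serious AEs above 5%, and the joint and serious/severe infection tables have no treatment-emergent condition in SAP v1.1 or in the shells shown. Relative to TEAE tables they add only pre-dose events that did not worsen, and no table reports treatment-emergent SAEs by arm.

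The effect is modest: 5% to 10% of background events with one to two weeks of pre-dose recording, at most 26%, and for SAEs probably a few subjects. This rests on a constant rate, full follow-up and an unknown recording start. The 26% should not be read as an estimate.

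Two further inferences are not supported. One is that the tables favour the drug: placebo and active arms are affected alike, so differences are diluted. The other is that every AESI table is affected: Table 14.3.2.2.4 cannot contain pre-dose events.

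The sponsor should confirm whether the AE notes in shells v1.1 are unchanged.

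**What to change.** In SAP Sections 9.1, 9.1.2 and 9.1.4, and in the notes to Tables 14.3.1.7, 14.3.2.1.1 to 14.3.2.1.4, 14.3.2.2.2 and 14.3.2.2.3, tabulate by arm the events that meet the Section 6.1.8 treatment-emergent definition. Joint events have no subsection of their own, so their window can be stated in Section 9.1. Keep pre-dose events in Listing 16.2.7.1 and in the SAE listing (Table 14.3.3.1). Table 14.3.2.2.4 needs no change.

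If showing all SAEs in dosed subjects is deliberate, say so in the SAP, keep those tables, and add a treatment-emergent row and a footnote giving the onset window.

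The cost is one filter, or one row and a footnote, plus a few sentences of SAP text. The drawback of the first option is that pre-dose SAEs no longer appear in any summary table; the second avoids that.

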6.3. Displays of Significant Adverse Events and Adverse Events of Special Interest

Table 14.3.2.2.1
Treatment Emergent Adverse Events Associated with Abnormal Liver by System Organ Class and Preferred Term Safety Population

Programming Notes:

- Same shell as Table 14.3.1.2. Change first row to be "Subjects with at least One TEAE Associated with Abnormal Liver". Remove references to TEAEs in footnote.
- Update Reference Listing to 16.2.7.3.
- A column for dosing (CC) will only be added if Stage 4 is initiated.

Table 14.3.2.2.2

Potential joint Related Adverse Events of Special Interest by System Organ Class and Preferred Term Safety Population

Programming Notes:

- Same shell as Table 14.3.1.2. Change first row to be "Subjects with at least One Potential Joint Related AESI"
- Add abbreviation for AESI = Adverse Event of Special Interest. Remove references to TEAEs in footnote.
- Update Reference Listing to 16.2.7.4
- A column for column dosing (CC) will only be added if Stage 4 is initiated.

Final 1.0 | 12-Jul-2023 | Page 74 of 205

[figure not shown]

Table 14.3.2.2.3 Serious and/or severe Infections by System Organ Class and Preferred Term Safety Population

Programming Notes:

- Same shell as Table 14.3.1.2. Change first row to be "Subjects with at Least One SAE or Severe AE Related to Infection". Add "SAE = Serious Adverse Event" to abbreviations. Remove references to TEAEs in footnote.
- Update Reference Listing to 16.2.7.5.
- A column for doing (CC) will only be added if Stage 4 is initiated.

[figure not shown]
Table 14.3.2.2.4

Anaphylactic Reactions, Hypersensitivity or Infusion-Related Reactions Leading to Discontinuation of IP by System Organ Class and Preferred Term Safety Population

Programming Notes:

- Same shell as Table 14.3.1.2. Change first row to be "Subjects with at Least One Anaphylactic Reaction, Hypersensitivity or Infusion-Related Reactions Leading to Discontinuation of IP". Remove references to TEAEs in footnote.
- Update Reference Listing to 16.2.7.6.
- A column for column dosing (cc) will only be added if Stage 4 is initiated.

Final 1.0 | 12-Jul-2023 | Page 75 of 205

[figure not shown]
